6. shift or night work;
7. medical problems that would be a direct cause of sleep complaints: moderate/severe sleep apnea, defined as an apnea-hypopnea index of ≥ 15 events per hour, periodic limb movement disorder defined as a periodic leg movement index ≥ 15 events per hour or restless legs syndrome;
8. other serious chronic conditions or exacerbation of chronic disorder preventing further participation.

Allowed Medications and Treatments

Regular therapy for cardiovascular diseases (beta-blockers, ACE-inhibitors, antiplatelets, antiarrhythmics).

Prohibited Medications and Treatments

The following medications are prohibited during the study and their administration will be considered a protocol violation:

substances affecting sleep (hypnotics, antidepressants, anxiolytics, antihistamine)

STUDY TREATMENTS

Method of Assigning Subjects to Treatment Groups

40 subjects meeting inclusion and exclusion criteria will be randomly assigned to one of treatment sequences (zopiclone-first group or BBT-I-first group) by card sorting method.

Blinding

The study will be open-label

Formulation of Test and Control Products

Formulation of Test Product 1

Brief behavioral therapy program will include a question-and-answer part; a didactic presentation of sleep regulation mechanisms; the review of causes of onset and chronification of illness; an examination of patient's sleep log; explanation of sleep restriction method and prescription of individual regimen of sleep; explanation of stimulus control method; sleep hygiene education; discussion of relaxation techniques. Participants will be supplied with 32 minute audio recording "Relaxation and refreshment session for insomnia" created for this study by Dr. [name] with verbal relaxing instructions with quiet musical composition behind it. Participants will be instructed to listen to this recording in headphones each day for 2-week BBT-I period after laying into bed and turning the light off.

Formulation of Test Product 2

Imovan is a trade name of ABC, developed by Sanofi winthrop industrie , for oral administration in the management of CI patients. Imovan is a white-colored tablet

Table 2: Formulation and Measured pH of Imovan

	Imovan
Active Ingredient, mg	Zopiclone, 7,5
Other ingredient, mg	Wheat amyllum, 60; natrii hydrophosphate dehydrate, 60; lactose monohydrate 31,575; sodium carboxymethyl starch, 4,95; magnesia stearate 0,975

Packaging and Labeling

All concomitant medication and concurrent therapies will be documented at baseline examination and at visit days. Dose, route, unit frequency of administration, and indication for administration and dates of medication will be captured.

Demographics

Demographic information (date of birth, gender) will be recorded at baseline examination.

Medical History

Relevant medical history, including history of current disease, other insomnia history, and information regarding underlying diseases will be recorded at baseline examination.

Physical Examination

A complete physical and neurological examination will be performed by the investigator who is a neurologist at baseline examination.

Vital Signs

Body temperature, blood pressure, pulse will be measured after resting for 5 minutes at baseline examination.

Polysomnography

1-night in-lab PSG (without adaptation night) will be performed at baseline examination. Standard polysomnography montage includes 6 monopolar electroencephalography (EEG) channels Fp₁A₂, Fp₂A₁, C₃A₂, C₄A₁, O₁A₂, O₂A₁; 1 submental electromyogram (EMG) channel; 2 electrooculogram (EOG) channels; 2 EMG channels of the right and left tibialis anterior muscles; 1 electrocardiogram channel; oronasal airflow pressure; thoracic and abdominal efforts; respiratory sound; oxygen saturation; body position with videomonitoring

Questionnaire

Subjects will be asked to fill in self-report questionnaires: Beck Depression Inventory (BDI), State-trait anxiety inventory (STAI), Toronto Alexithymia Scale – short version TAS-20, Big Five Questionnaire (BFQ-2R), Pittsburg Sleep Quality Index (PSQI), Insomnia Severity Index (ISI), Dysfunctional beliefs about sleep scale (DBAS), Sleep hygiene index (SHI) at baseline examination.

During the next 4 visits participants will repeatedly undergo diagnostic tests including BDI, STAI, PSQI, ISI, DBAS, SHI.

Adverse Events

Information regarding occurrence of adverse events will be captured throughout the study. Duration (start and stop dates and times), severity, outcome, treatment and relation to study drug will be recorded on the case report form (CRF).

Clinical Laboratory Measurements

β -adrenoreactivity test

Peripheral blood sample will be collected in a sterile tube and tested in lab for erythrocyte membranes β -adrenoreactivity by a method based on detection of adrenoreceptor sensitivity to-endogenous catecholamines

EVALUATIONS BY VISIT

Visit 1 (Day 1/Week 1/ Month 1)

1. Review the study with the subject and obtain written informed consent.
2. Record demographics data.
3. Record medical history, including a history of insomnia, diagnosis date, and prior treatments.
4. Record concomitant medications.
5. Perform a complete physical and neurological examination.
6. Perform and record vital signs.
7. Perform and record Polysomnography
8. Perform questionnaire completion
9. Perform and record results of β -adrenoreactivity testing.
10. Randomize subject for zopiclone-first or BBT-I-first group.
11. Writing Imovan prescription for zopiclone-first group subjects
12. First BBT-I session BBT-I-first group subjects
13. Initiate subject diary.

Visit 1.2 (for subjects of BBT-I-first group) (Day 8/Week 2/ Month 1)

1. Second BBT-I session

Visit 2 (Day 14/Week 2/Month 1)

1. Record any Adverse Experiences and/or Review subject diary for adverse experiences and dosing compliance.
2. Perform questionnaire completion
3. Perform and record results of β -adrenoreactivity testing.

Visit 3 (Day 28/Week 4/Month 1)

1. Record any Adverse Experiences and/or Review subject diary for adverse experiences and dosing compliance.
2. Perform questionnaire completion
3. Perform and record results of β -adrenoreactivity testing.
4. Writing Imovan prescription for BBT-I-first group subjects
5. First BBT-I session for zopiclone-first group subjects

Visit 3.2 (for subjects of zopiclone-first group) (Day 35/Week 5/ Month 2)

1. Second BBT-I session

Visit 4 (Day 42/Week 6/Month 2)

1. Record any Adverse Experiences and/or Review subject diary for adverse experiences and dosing compliance.
2. Perform questionnaire completion
3. Perform and record results of β -adrenoreactivity testing.

Visit 5 (Day 56/Week 8/Month 2)

1. Record any Adverse Experiences and/or Review subject diary for adverse experiences and dosing compliance.
2. Perform questionnaire completion
3. Perform and record results of β -adrenoreactivity testing.
4. Medical consultation for treatment and health maintenance

Early Withdrawal Visit

1. Record any Adverse Experiences and/or Review subject diary for adverse experiences and dosing compliance.
2. Perform questionnaire completion
3. Perform and record results of β -adrenoreactivity testing.
4. Medical consultation for treatment and health maintenance

ADVERSE Experience REPORTING AND DOCUMENTATION**Adverse Events**

Subjects withdrawn from the study treatment will be replaced. Subjects withdrawn from the study after Visit 5 but prior to Visit 6 won't be replaced.

Protocol Violations

Protocol violations for this study include, but are not limited to, the following:

- Failure to meet inclusion/exclusion criteria

- Use of a prohibited concomitant medication
- Non-compliance with study drug regimen, and questionnaires completion

Failure to comply with Good Clinical Practice (GCP) guidelines will also result in a protocol violation. If a protocol violation occurs, a Protocol Violation Form detailing the violation will be generated.

DATA SAFETY MONITORING

There will be no data monitoring committee

STATISTICAL METHODS AND CONSIDERATIONS

A Statistical Analysis Plan (SAP) is written describing all analyses that will be performed.

Data Sets Analyzed

All subjects matching inclusion and exclusion criteria who will complete at least one treatment course (BBT-I or medication) and fill in questionnaires prior and after the treatment will be included in the safety analysis.

Demographic and Baseline Characteristics

The following demographic variables at screening will be summarized by dose level: gender, age, height and weight. Continuous variables will be presented in means and standard deviation ($M \pm SD$).

Analysis of Primary Endpoint

Statistical significance of differences between ISI level before and after treatment for both treatment methods will be evaluated with Student's t-test after confirmation of normal variable distribution by Kolmogorov-Smirnov test. For continuous variables with distribution other than normal Mann-Whitney U-test will be used. For comparison of the proportions Pearson chi-squared test will be performed.

Criterion of response to the treatment is defined as the reduction of ISI score reduction of >7 points from baseline. This criterion is indicative of moderate improvement and validated as clinically significant (Morin, Belleville & Belanger, 2011). As well the criterion corresponds to approximately 1 standard deviation of the pretreatment values (Cohen effect size of approximately 1.0). Remission criterion is defined as final ISI score of 7 points or less. Nonresponse criterion is defined as ISI score decrease of ≤ 7 points from baseline.

Analysis of Secondary Endpoints

Statistical significance of differences between BDI, STAI, PSQI, DBAS, SHI, β -adrenoreactivity level, sleep diary data before and after treatment for both treatment methods will be evaluated with Student's t-test after confirmation of normal variable distribution by Kolmogorov-Smirnov test. For continuous variables with distribution

other than normal Mann-Whitney U-test will be used. For comparison of the proportions Pearson chi-squared test will be performed.

Based on the response criterion participants will be divided into two groups: responders and nonresponders for each method of treatment. Comparison of responders and nonresponders baseline quantitative characteristics (polysomnographic, antropometric, psychometric) will be performed using Student's t-test (for normal data distribution) or Mann-Whitney U-test (for abnormal data distribution). Statistical significance will be set at a p-value less 0,05.

Safety and tolerability data will be summarized by treatment group. Adverse events will be tabulated by treatment group and include the number of patients for whom the event occurred, the rate of occurrence, and the severity and relationship to study drug.

Interim Analysis

Interim statistical analysis will be performed after 20 patients complete the study protocol.

Sample Size and Randomization

The number of subjects planned to be enrolled is 40. This is a representative sample for study of treatment effects. The crossover design of the study will allow us to compare two therapeutic approaches with a relatively small sample size and to determine the predictors of effectiveness for each treatment.

DATA COLLECTION, RETENTION AND MONITORING

Data Collection Instruments

The Investigator will prepare and maintain adequate and accurate source documents designed to record all observations and other pertinent data for each study subject. The information corresponding to each visit will be entered to the study database and to paper CRF.

The Investigator is responsible for all information collected on subjects enrolled in this study. All data collected during the course of this study will be reviewed and verified for completeness and accuracy by the Investigator.

Data Management Procedures

The data will be entered into a validated database. The Investigator is responsible for data processing, in accordance with procedural documentation.

All procedures for the handling and analysis of data will be conducted using Microsoft Office Excel 2007 and STATISTICA 7

Data Quality Control and Reporting

The Investigator is responsible for data collection, validation, processing and reporting in accordance with procedural documentation.

Archival of Data

The database is safeguarded against unauthorized access by established security procedures; appropriate backup copies of the database and related software files will be maintained. Databases will be backed up by the Investigator in conjunction with any updates or changes to the database.

Availability and Retention of Investigational Records

The Investigator must make study documents (patient files, signed informed consent forms, copies of CRFs, questionnaires, sleep diaries) accessible to the monitor, IRB/IEC, and Regulatory Agency inspectors upon request. A file for each subject will be maintained that includes the signed Informed Consent, HIPAA Authorization and Assent Form and copies of all source documentation related to that subject. The Investigator must ensure the reliability and availability of source documents from which the information on the CRF is derived.

All study documents (patient files, signed informed consent forms, copies of CRFs, questionnaires, sleep diaries) must be kept secured for the whole study period and two years after study completion.

Subject Confidentiality

The study is open-label. All subjects will give written consent allowing their personal data to be maintained and used for scientific purposes and published. In order to maintain subject confidentiality, only a subject number will identify all study subjects on data reports.

ADMINISTRATIVE, ETHICAL, REGULATORY CONSIDERATIONS

The study will be conducted according to the WMA Declaration of Helsinki - Ethical Principles for Medical Research Involving Human Subjects October 2013; Ethical Issues in Patient Safety Research: Interpreting existing guidance, WHO, 2013; Consolidated Guideline for good clinical practice (ICH), 1996; European Union Council and Parliament guidelines (for instance, Guidelines on the practice of ethics committees in medical research, 2007; The Constitution of the Russian Federation (Article 21); OrderN 323-FZ «About the Fundamentals of Health Protection of the Russian Federation citizens» 21 November 2011; Order N 61-FZ “About the drug use” from 22 December 2014; The Russian Federation National Standard «Good Clinical Practice» (National Standard P 52379-2005); and local regulations

All study records will be kept in a locked file. Only a subject number will identify all study subjects on data reports. The Investigator is responsible for confidentiality of subjects' personal data.

Protocol Amendments

Any amendment to the protocol will not be implemented without prior written IRB/IEC approval.

Institutional Review Boards and Independent Ethics Committees

The protocol will be reviewed and approved by the IRB/IEC of I.M. Sechenov Moscow State Medical University on 18th March, 2015. Serious adverse experiences regardless of causality will be reported to the IRB/IEC in accordance with the standard operating procedures and policies of the IRB/IEC, and the Investigator will keep the IRB/IEC informed as to the progress of the study. The Investigator will obtain assurance of IRB/IEC compliance with regulations.

Any documents that the IRB/IEC may need to fulfill its responsibilities (such as protocol, protocol amendments, Investigator's Brochure, consent forms, etc.) will be submitted to the IRB/IEC. The IRB/IECs' written unconditional approval of the study protocol and the informed consent form will be in the possession of the Investigator before the study is initiated. This approval must refer to the study by exact protocol title and number and should identify the documents reviewed and the date of review.

Protocol and/or informed consent modifications or changes may not be initiated without prior written IRB/IEC approval. Such modifications will be submitted to the IRB/IEC and written verification that the modification was submitted and subsequently approved should be obtained. The IRB/IEC must be informed of revisions to other documents originally submitted for review; serious and/or unexpected adverse experiences occurring during the study in accordance with the standard operating procedures and policies of the IRB; new information that may affect adversely the safety of the patients of the conduct of the study.

Informed Consent Form

Informed consent will be designed in accordance with the WMA Declaration of Helsinki - Ethical Principles for Medical Research Involving Human Subjects October 2013; Ethical Issues in Patient Safety Research: Interpreting existing guidance, WHO, 2013; Consolidated Guideline for good clinical practice (ICH), 1996; European Union Council and Parliament guidelines (for instance, Guidelines on the practice of ethics committees in medical research, 2007; The Constitution of the Russian Federation (Article 21); Order N 323-FZ «About the Fundamentals of Health Protection of the Russian Federation citizens» 21 November 2011; Order N 61-FZ «About the drug use» from 22 December 2014; The Russian Federation National Standard «Good Clinical Practice» (National Standard P 52379-2005); and local regulations.

The consent form generated by the Investigator will be approved by the IRB/IEC of I.M. Sechenov Moscow State Medical University on 18th March, 2015. The written consent

document embodies the elements of informed consent as described in the International Conference on Harmonisation and comply with local regulations.

A properly executed, written, informed consent will be obtained from each subject prior to entering the subject into the trial. Information should be given in both oral and written form and subjects must be given ample opportunity to inquire about details of the study. A copy of the signed consent form will be given to the subject and the original will be maintained with the subject's records.

Publications

The preparation and submittal for publication of manuscripts containing the study results shall comply with all applicable privacy laws, including, but not limited to, the Health Insurance Portability and Accountability Act of 1996.

Investigator Responsibilities

By signing the Agreement of Investigator form, the Investigator agrees to:

1. Conduct the study in accordance with the protocol, except when to protect the safety, rights or welfare of subjects.
2. Personally conduct the study
3. Ensure that the requirements relating to obtaining informed consent and IRB review and approval meet federal guidelines.
4. Ensure that all associates, colleagues and employees assisting in the conduct of the study are informed about their obligations in meeting the above commitments.
5. Maintain adequate and accurate records and to make those records available for inspection of IRB/IEC.
6. Ensure that an IRB will be responsible for initial and continuing review and approval of the clinical study.
7. Promptly report to the IRB all changes in the research activity and all unanticipated problems involving risks to subjects or others.
8. Seek IRB approval before any changes are made in the research study, except when necessary to eliminate hazards to the subjects.
9. Comply with all other requirements regarding the obligations of clinical investigators and all other pertinent requirements listed in regulatory documents.

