
STATISTICS Primary Analysis Plan
	
Analysis of insomnia treatment will be conducted only for patients matching inclusion and exclusion criteria who will complete at least one treatment course (BBT-I or medication) and fill in questionnaires prior and after the treatment. Continuous variables will be presented in means and standard deviation (M±SD). Categorical and rank variables will be presented as percentages.
 
Statistical significance of differences between group for continuous variables will be evaluated with Student’s t-test after confirmation of normal variable distribution by Kolmogorov-Smirnov test.
 
For continuous variables with distribution other than normal Mann-Whitney U-test will be used. For comparison of the proportions Pearson chi-squared test will be performed.
 
Criterion of response to the treatment is defined as the reduction of ISI score reduction of >7 points from baseline. Remission criterion is defined as final ISI score of 7 points or less. Nonresponse criterion is defined as ISI score decrease of ≤7 points from baseline. Based on these dichotomic values participants will be divided into two groups: responders and nonresponders for each method of treatment.
 
Comparison of responders and nonresponders baseline quantitative characteristics will be performed using Student’s t-test (for normal data distribution) or Mann-Whitney U-test (for abnormal data distribution). Statistical significance will be set at a p-value less 0,05.

Rationale for Number of Subjects
	
Study design allows to compare two therapeutic approaches with a relatively small sample size and to determine the predictors of effectiveness for each treatment. Thus 40 patients get 2 therapeutic approaches. This is the representative sample size enough to produce normal variable distribution for further parameter statistical analysis.

PURPOSE OF THE INVESTIGATION

Name of investigational method

Brief behavioral therapy program
Imovan (zopiclone)

Intended use of the investigational method

2-week Brief behavioral therapy will be performed in two 1 hour session for treatment of chronic insomnia (CI)

Imovan (zopiclone) in a dose of 7,5 mg has to be taken 30 minutes before bedtime for two weeks

Overview of Clinical Studies

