To test the effectiveness of short BBT-I program for chronic insomnia in comparison with zopiclone in Russian population.

Secondary Objectives

Identification of anthropometric, psychological and polysomnographic predictors of effectiveness of each method.

STUDY DESIGN

Study Overview

Prospective randomized crossover study. In accordance with this design every patient will receive two different treatment courses in random sequence: zopiclone or structured educational program (BBT-I) delivered in two sessions. Patients of the zopiclone-first group will receive the medication therapy for the first two weeks followed by educational program. Patients of the BBT-I-first group will receive two-week educational program followed by medication therapy.

Each treatment course will be separated by 2-weeks washout period that will provide the opportunity to evaluate the sustainability of treatment effect.

The total duration of the study will be 8 weeks with 6 visits including 1 night polysomnography (PSG), 2 face-to-face structured educational program sessions and 5 diagnostic interviews. Total duration of the study will be 2 years.

Criteria for evaluation

Primary Efficacy Endpoint

Proposed primary efficacy endpoint is change of insomnia severity index (ISI) after treatment. Criterion of response to the treatment will be defined as the reduction of ISI score reduction of >7 points from baseline. This criterion is indicative of moderate improvement and validated as clinically significant (Morin, Belleville & Belanger, 2011). Remission criterion will be defined as final

ISI score of 7 points or less. Nonresponse criterion will be defined as ISI score decrease of ≤ 7 points from baseline.

Secondary Efficacy Endpoints

1. Insomnia severity index self reported insomnia symptoms severity . Each item is scored 0 (no problem) - 4 (very big problem) with total between 0-28 (absence of insomnia (0-7); sub-threshold insomnia (8-14); moderate insomnia (15-21); and severe insomnia (22-28).
2. Beck Depression Inventory. 21-item questionnaire assessing (on 4-point Likert scales) the intensity of depressive symptoms in the past week
3. State-trait anxiety inventory. 2-part questionnaire assessing state (situational) and trait anxiety. Both situational and trait parts comprise 20 items rated on a 4-point Likert scale.
4. Dysfunctional beliefs about sleep scale. questionnaire assessing sleep related cognitions in 16 item rated on a 10-point Likert scale.

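### The primary and secondary tests are before/after tests within each method, which cannot attribute change to the method and do not answer the comparative objective

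*Combined protocol and SAP*

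**What the plan says.** Under Analysis of Primary Endpoint: "Statistical significance of differences between ISI level before and after treatment for both treatment methods will be evaluated". The test is Student's t after a Kolmogorov-Smirnov check, with Mann-Whitney U as the fallback. Analysis of Secondary Endpoints repeats this for BDI, STAI, PSQI, DBAS, SHI, β-adrenoreactivity and diary data: "sleep diary data before and after treatment for both treatment methods will be evaluated". Neither section says whether the t-test is paired, and neither has a period or sequence term.

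The only between-group wording for outcome scores is in the synopsis: "Statistical significance of differences between group for continuous variables will be evaluated with Student". It does not say whether the groups are methods or sequences, or whether scores or changes are compared.

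The Primary Objective is comparative: "To test the effectiveness of short BBT-I program for chronic insomnia in comparison with zopiclone in Russian population". In the Study Overview, "every patient will receive two different treatment courses in random sequence: zopiclone or structured educational program (BBT-I) delivered in two sessions". Evaluations by Visit starts both sequences on treatment at Visit 1 (Day 1). On the washouts: "Each treatment course will be separated by 2-weeks washout period that will provide the opportunity to evaluate the sustainability of treatment effect".

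**The concern.** A before/after mean within one method is the effect of that method plus whatever would have changed over the same two weeks without it. Patients enrol while they have an active complaint, know what they receive, and fill in self-report scales at baseline and at four further visits. Some improvement common to both courses is therefore plausible. If it occurs, the tests named as the primary and secondary analyses can be significant for both methods when neither adds anything. Nothing in the plan limits how such a result may be read.

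The tests also miss the question. Two within-method p-values, whether both are significant or only one is, do not test the difference between BBT-I and zopiclone.

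**Working it through.** **The plan's own figure.** The sample size is 40. No power, target difference or SD of change is given with it, so it cannot be reproduced.

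**What can be estimated.** Let π1 and π2 be the shared change in courses 1 and 2, and τB and τZ the effects of BBT-I and zopiclone. Leaving carry-over aside, the mean changes are:

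| Sequence | Course 1 | Course 2 |
|---|---|---|
| BBT-I first | π1 + τB | π2 + τZ |
| Zopiclone first | π1 + τZ | π2 + τB |

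Add any constant to both π and subtract it from both τ: all four cells stay the same. So τB and τZ cannot be estimated separately, with or without a period term in the model. Their difference can. Course 1 minus course 2 has mean (π1 − π2) + (τB − τZ) in one sequence and (π1 − π2) − (τB − τZ) in the other. Subtracting gives 2(τB − τZ), and the shared change drops out.

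**Inputs for the illustration.**
- n = 40, two-sided 0.05 (the plan gives 0.05 but not the sidedness).
- SD about 7: Analysis of Primary Endpoint equates the 7-point criterion with about 1 SD of pretreatment values.
- Assumed: shared drop g of 1, 2 or 3 ISI points in each course; before/after correlation r = 0.5, varied from 0.3 to 0.7; τB = τZ = 0. The before score is taken at the start of each course.

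**Paired reading.** SD of change = 7 × √(2(1 − 0.5)) = 7. The noncentrality is g / (7/√40) = g / 1.107, that is 0.90, 1.81 and 2.71 for 1, 2 and 3 points, on 39 degrees of freedom.

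**Unpaired reading.** The test uses SE = 7 × √(2/40) = 1.565 and a critical value of 1.991 (78 degrees of freedom). Because the scores are in fact correlated, the statistic has SD of about √(1 − r) = 0.707. For g = 3, (1.991 − 3/1.565)/0.707 = 0.105, which gives a rejection probability of about 46%.

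Probability that one method is significant with no treatment effect:

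| Shared drop | Paired, r 0.5 | Paired, r 0.3 to 0.7 | Unpaired, r 0.5 | Unpaired, r 0.3 to 0.7 |
|---|---|---|---|---|
| 1 | 14% | 12–21% | 3% | 1–5% |
| 2 | 42% | 32–62% | 16% | 10–20% |
| 3 | 75% | 61–93% | 46% | 45–47% |

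Simulation of a 20/20 crossover (20,000 trials per setting, SD 7, r 0.5) agrees within about one percentage point. On the paired reading both methods are significant in about 18% of trials at 2 points and 57% at 3 points. The period-adjusted between-method contrast rejects in about 5% at every drop. With a shared drop of 4 points in course 1 and none in course 2, each paired before/after test rejects in about 39% and the period-adjusted contrast in 4.8%.

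**The case against.** Several points on the other side have force.

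- The text never says that the t-test is paired, and the Mann-Whitney fallback is an independent-samples test. A reader might infer that the error is always far above nominal. It is not: on the unpaired reading a 1-point drop gives about 3%, below 5%. At 2 and 3 points the rate exceeds 5% on either reading.
- The shared drop and the correlation are assumptions. The inclusion criteria set no ISI threshold, so regression to the mean cannot be sized. This limits the figures; the confounding does not depend on them.
- A reader might infer that the plan will declare each method effective. No section says so. The objective is comparative, and the Overview of Clinical Studies already treats both approaches as having proven efficacy. A nonzero mean change is also a true statement about change; the error lies in attributing it to the method. But the plan makes this test its primary analysis and sets no limit on its interpretation.
- A reader might infer that there is no off-treatment time at all. Washouts follow each course, with questionnaires at Visits 3 and 5. They come after treatment and serve to judge persistence, so they are not a clean reference.
- The synopsis does mention a between-group test, so comparison is not wholly absent. As written it cannot be carried out without deciding what is compared.
- A reader might infer that a time term would repair the before/after test. The cell means above show that it would not.

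**Conclusion.** The concern holds in a limited form. The stated primary and secondary tests cannot attribute change to either method and do not address the primary objective. This follows from the design and the wording and needs no numerical assumption. How often it would mislead does need assumptions: in the illustration, about 14% to 75% per method for shared drops of 1 to 3 points if paired, and about 3% to 46% if unpaired. The documents do not support a claim that the rate is inflated in every case. The between-method contrast is protected from shared change, though it still assumes that carry-over past the washout does not differ between methods.

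**What to change.** In Analysis of Primary Endpoint and Analysis of Secondary Endpoints:

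1. Report the mean before-to-after change for each method with a 95% confidence interval as description only, and state that no conclusion of effectiveness rests on it.
2. Name the BBT-I versus zopiclone difference in change, adjusted for period, as the test to which p<0.05 applies for ISI and the secondary scores. One simple form is a two-sample t-test by sequence on course 1 change minus course 2 change. The sequences are independent groups, so the plan's Mann-Whitney fallback would fit there. State which visit is the before measurement for the second course.
3. Align the synopsis wording with this contrast.
4. Leave the responder/nonresponder comparisons and their p<0.05 criterion unchanged, since they serve the secondary objective. Restricting the criterion to between-method differences throughout would remove it from them by accident.

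The cost is wording, with no new patients or data. Patients who complete only one course enter the plan's analysis set but would not contribute to the simple form of the contrast, so their handling should be stated. The trial gives up a formal claim that each method on its own improves the scores, which this design cannot support.
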